4.1. General Methodology

Continuous data will be described using descriptive statistics including patient count (n), mean, standard deviation (SD), median, minimum, and maximum. Categorical data will be described using the patient count and percentage in each category. The percentage will be suppressed when the count is zero for a category in order to draw attention to the non-zero counts. Where specified on the table shells, a row denoted "Missing" is to be included in count tabulations to account for dropouts and missing values. The denominator for all percentages will be the number of patients in that treatment arm within the analysis population of interest, unless otherwise specified.

Patients will be identified in the listings by the patient identification number concatenated with the investigator/site number. Data will be displayed in all listings sorted by patient identification number concatenated with the investigator/site number. Data listings, unless otherwise specified, will include all patients who provide consent to participate in the study.

Unscheduled results will not be included in the summary tables except for determining Baseline values for efficacy and safety evaluations and the handling of laboratory data both at Baseline and during treatment (see Section 4.2). For patients discontinuing from the study, planned study visit data that are collected at the early termination visit will be included in by-visit summaries in the summary tables or figures (e.g. PRO questionnaires) using the serial next visit number associated with what would have been the patient's next scheduled visit. Thus, for example, a patient discontinuing from the study after Treatment Visit 2 would have efficacy and safety data obtained at the study termination visit treated as Treatment Visit 3 results. Data listings will include all data from scheduled, repeated, unscheduled and early termination visits.

All p-values will be rounded to three decimal places. If a p-value is less than 0.001 it will be reported as "<0.001." If a p-value is greater than 0.999 it will be reported as ">0.999." Point estimates of the parameter of interest will be generated along with, where appropriate, 95% confidence intervals.

All analyses will be conducted using SAS Version 9.2 or higher.

4.2. Baseline, Study Day and Analysis Visit Windows

Unless otherwise specified, "Baseline" for efficacy and safety information is defined as the last non-missing evaluation taken prior to the first dose of study medication during the TR03 extension study (including repeated and unscheduled assessments).

For variables that require the analysis of change from baseline, the post-baseline assessment value minus the baseline assessment value will be used to derive change from baseline value. If either value is missing then the change from baseline will also be missing.

When study day is used for display or in comparisons, the following algorithm will be used:

- Study day = date of assessment – date of first dose of study medication + 1, if the date of the assessment is on or after the date of first dose;
- Study day = date of assessment – date of first dose of study medication, if the date of the assessment is prior to the date of first dose.

No analysis visit windows will be defined for this study, i.e., by-visit assessments will be based on the designated scheduled visit number associated with the data recorded for the endpoint of interest.

4.3. Sample Size

As this is a safety extension study for which patients will be recruited from patients who have completed parent study TR03, the sample size cannot be predicted. No formal sample size

calculations have been performed and no inferential statistics are planned. The maximum number of patients will not exceed the number of patients who completed TR03.

4.4. Randomization, Stratification, and Blinding

Patients will not be randomized into this study. For this study, patients will retain their study number from the TR03 study.

4.5. Pooling of Study Sites

No *a priori* pooling of sites is planned for this study as no formal statistical testing is planned.

4.6. Analysis Populations

4.6.1. All Enrolled

An enrolled patient is one who provides consent to participate in the TR03ext study.

4.6.2. Safety

The Safety population will consist of all enrolled patients who have received a single dose of study medication in the TR03 extension study. The Safety population will be used to evaluate the safety and efficacy endpoints defined for this study.

Patients will be summarized in a single nalbuphine treatment group.

4.7. Methods for Handling Dropouts and Missing Data

No replacement or imputation of missing data will be conducted for this study.

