3.2. Premature Discontinuation of Study Drug Treatment

3.2.1. Premature Discontinuation of Study Drug Treatment Associated with Failure-to-Improve Criterion

Patients who meet failure-to-improve criterion during the conduct of the study, will stop taking study medication.

The Failure-to-Improve criteria are as follows: Beginning on Treatment Period Visit 3 (TV3), and at every subsequent Treatment visit, patients with a worst itch NRS score \geq the worst itch NRS score at Visit 1a (or at Visit 1b in the case of patients who require the OV period) will be discontinued from study drug. Patients discontinued from study drug are to undergo the End of Treatment Visit (TV14), the Washout/Safety Follow-up Period assessment in two weeks, and receive a follow-up telephone contact 30 days following end of study drug dosing for final safety assessment.

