8.1. Change from Baseline in PRO Measures

For the PRO measures detailed in the subsections below, change from baseline analysis will be performed.

Summary statistics will be generated for each PRO measure for total patients and for patients by their TR03 core study treatment at Baseline, each Treatment Period study visit, the Washout and Safety Follow-up visit and LOV and for change from baseline in each PRO measure at each Treatment Period study visit, the Washout and Safety Follow-up visit and LOV.

Means and change from baseline means for each PRO with a continuous response will be presented in bar charts for all patients by study visit.

Values from all PRO measures will be presented in data listings.

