8.4. Failure-to-Improve Criteria

Beginning with the TV3 visit and at each subsequent treatment visit (up to and including the TV13 visit) the number and percentage of patients who meet failure-to-improve criteria will be summarized.

The visit at which failure-to-improve criteria are met will be presented in a data listing for the safety population.

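### From about TV5 the by-visit itch means overstate improvement: patients are stopped on the same NRS that is averaged, and no planned summary gives the on-drug result for all treated patients

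*SAP*

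**What the plan says.** - **Removal.** Section 3.2.1: "Patients who meet failure-to-improve criterion during the conduct of the study, will stop taking study medication". The check is repeated: "Beginning on Treatment Period Visit 3 (TV3), and at every subsequent Treatment visit, patients with a worst itch NRS score" at or above the baseline value "will be discontinued from study drug". Section 8.4 tabulates failures from TV3 up to and including TV13.
- **Missing data.** Section 4.7: "No replacement or imputation of missing data will be conducted for this study". Section 4.2: "If either value is missing then the change from baseline will also be missing".
- **Display.** Section 8.1 plans summaries "for change from baseline in each PRO measure at each Treatment Period study visit, the Washout and Safety Follow-up visit and LOV". Means and mean changes "will be presented in bar charts for all patients by study visit".
- **Termination data.** Section 4.1 assigns data from the early termination visit to the patient's next scheduled visit, and to no later one.
- **LOV.** Section 8 defines it as the last post-baseline value, with the washout visit included.
- **Caveat.** Section 8.5 warns that early discontinuation may confound the rescue medication results. Section 8.1 has no such warning.

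**The concern.** The variable that decides who leaves is the variable being averaged. Once patients at or above baseline have been taken off drug and have dropped out of the by-visit table, the remaining mean is pulled down even if nobody's underlying itch has changed. Change from baseline by visit is a listed secondary endpoint (section 3.3.2). With no control arm, the trajectory is the main thing a reader has to go on. A chart labelled as all patients that falls steadily to the end of treatment would be read as durable benefit, when part of the fall, of unknown size, is selection.

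**Working it through.** The SAP states no effect size, variability or sample size (section 4.3), so there is no figure of its own to reproduce.

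**Who contributes at each visit.** Let Y0 be baseline NRS, Yv the NRS at visit v, and T the first visit from TV3 to TV13 with Yv >= Y0. That is 13 - 3 + 1 = 11 checks. With the next-visit rule of section 4.1, the observed-case mean at visit v is taken over patients with T >= v or T = v - 1, that is, everyone below baseline at TV3 through TV(v - 2).
- TV3 and TV4: everyone contributes, so there is no selection.
- TV5: only patients below baseline at TV3, plus none of those stopped there. Selection starts here.
- Each later visit adds one more condition.

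If termination data were not reassigned, the effect would start one visit earlier, at TV4.

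**Assumptions, none from the SAP.** Constant true itch per person, mean 7, between-person SD 1.2; visit noise with within-person SD 0.5 to 2.0; no dropout other than the rule. **From the SAP:** integer scale 0 to 10 (section 8.1.1), entry at NRS >= 5 (section 3.1), the removal rule, and the next-visit rule.

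**Mean change at TV13, next-visit rule applied**

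| Within-person SD | Inert drug: observed | truth | excess | 1.5-point effect: observed | truth | excess |
|---|---|---|---|---|---|---|
| 1.0 | -1.88 | -0.09 | -1.79 | -2.45 | -1.57 | -0.88 |
| 1.5 | -2.47 | -0.23 | -2.24 | -3.08 | -1.69 | -1.39 |
| 2.0 | -2.91 | -0.45 | -2.46 | -3.60 | -1.86 | -1.74 |

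Truth is the mean change if everyone were followed; excess is observed minus truth. The non-zero truth for an inert drug is regression to the mean from the entry threshold. At within-person SD 0.5 the inert-drug figure is about -1.1 against a truth near 0.0, and a 1.5-point effect is overstated by about 0.25. At that same SD a 3-point effect shows almost no bias. If the termination value is taken to be the failing reading itself rather than a new reading, the inert-drug figure at SD 2.0 is about -2.6 instead of -2.9. For SD 1.0 to 2.0, about 5% of patients still contribute at TV13 under an inert drug, and 21 to 36% under the 1.5-point effect.

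**Other assumptions, inert drug.** Person means and SDs of 7/1.5, 6/2 and 8/1, within-person SD 0.5 to 2, noise correlation 0 or 0.5: TV5 -0.5 to -1.6, TV8 -0.9 to -2.5, TV14 -1.1 to -3.3, against 0.0 to -0.7 at TV14 with full follow-up. The direction was the same in every scenario.

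**LOV.** For an inert drug it gives +0.1 to -0.7 under this second set, against 0.0 to -0.7 with full follow-up, so it is close. Under the first set, with a 1.5-point effect that wears off at washout, it gives about 0.0 to -0.5 against a true on-drug change of -1.5 to -1.9. The last on-treatment value errs the other way: +0.2 to +1.0 for an inert drug (second set), because patients are stopped on a high reading.

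**The case against.** **The attrition would be visible.** The plan gives n with every continuous summary (section 4.1), failure-to-improve counts by visit (section 8.4) and discontinuations for lack of efficacy or adverse events by visit (section 8.6). This stands: a collapse in numbers would show. But these counts signal the problem without correcting the mean, and they are not tied to the bar charts.

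**LOV retains removed patients.** This also stands, and for an inert drug LOV shows almost no false improvement. It fails only for a drug that works, which is the case where the size of the benefit matters.

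**The study is an uncontrolled, descriptive safety extension.** True. Imputing nothing is a legitimate choice in such a study, and regression to the mean would remain after any repair. The objection is to the label and the missing companion summary, not to section 4.7 taken alone.

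**Stronger readings to avoid.** A reader might infer that the charts will show falling itch whatever the drug does. The SAP does not support that: the size depends on variability and drug effect that it does not give, and can be near zero. A reader might also infer that the 6-month, 9-month and completer groups repeat the same selection. They apply to VRS, ItchyQoL and PAS (sections 8.1.3, 8.1.5, 8.1.8), not to worst itch NRS, so selection there is indirect, was not simulated, and each group stands beside all patients. The washout change in section 8.2 is limited to patients who complete through End of Treatment and carries related selection.

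**Conclusion.** The point holds in a limited form. The removal rule together with observed-case means makes the by-visit worst itch results too favourable from about TV5. Under the first set of assumptions the TV13 mean for an inert drug is about -1.1 to -2.9 instead of 0.0 to -0.5, and a true 1.5-point effect is overstated by about 0.25 to 1.7 points. The direction follows from the SAP's own rules; the size rests wholly on assumed itch variability and drug effect. By-visit means overstate, LOV understates an effective drug, and no planned summary gives the on-drug result for all treated patients. Average itch NRS is affected through its link with worst itch. Nothing here bears on the primary safety endpoint or on whether the stopping rule is appropriate.

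**What to change.** In section 8.1, for worst and average itch NRS:

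1. At each Treatment Period visit, add the percentage of patients on drug with NRS below baseline, counting those who stopped early as not improved. The denominator should be all Safety-population patients scheduled for that visit given their entry. A patient who spends the full 12 weeks in the Observation Period has at most 50 - 12 = 38 weeks of treatment and must not be counted as a failure at visits never scheduled. This row needs no model and is free of the selection; it measures sustained improvement, so it reads low (about 4% at TV13 in the inert-drug runs).
2. Add an on-treatment LOV that excludes the washout visit, with a note that it is biased in the unfavourable direction because patients are stopped on a high reading.
3. Show the cumulative number removed for failure-to-improve beside each by-visit mean and bar chart.
4. Extend the section 8.5 caveat to the itch means and to the duration and completer groups.

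A mixed model for repeated measures using all on-treatment visits, including the failing one, may be added as supportive if enough patients remain. In very large simulations a comparable regression came close to the truth (inert drug, TV13: -0.12, -0.33 and -0.55 against -0.09, -0.23 and -0.45). However, regressing TV13 on baseline and TV3 to TV12 needs 12 coefficients, and with an assumed 100 patients and 2 to 8% remaining only 2 to 8 would inform it. It handles only removals that depend on recorded NRS and does not remove regression to the mean.

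Cost: SAP wording, two extra tables, and less favourable later-visit figures. Trial conduct is unchanged.

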4.8. Multiple Comparisons/Multiplicity Considerations

There will be no consideration for multiple comparisons/multiplicity for this study as no inferential analyses will be performed.

4.9. Examination of Subgroups

No *a priori* planned subgroup analyses are specified and none will be performed.

4.10. Data Display Treatment and Other Descriptors

Unless otherwise noted, TR03 extension study treatments will be presented in all tables, listings and figures (TLFs) as: All Patients. Additionally, TR03 core study randomized treatments will be presented as: Nalbuphine 90 mg, Nalbuphine 180 mg, and Placebo.

For measurements collected at multiple study visits, visit and week number will be used in all TLFs. Baseline results (as described in Section [4.2](#)) will be displayed as “Baseline.”

4.11. Changes in the Planned Analysis

Section 9.7.7.5 of the protocol discusses a 9-item sleep problems index that can be generated for the MOS Sleep Scale-R. This, however, will not be implemented. SAP [Section 8.1.6](#) describes the summaries that will be presented for the MOS Sleep Scale-R.

Section 19.6 of the protocol states that opioid medication usage will be tabulated separately from all other concomitant medications. Instead, opioid medication usage will be tabulated with all other concomitant medications as discussed in SAP Section [7.1](#).

Section 19.7 of the protocol states that mean dose during the treatment period will be summarized. Instead, as discussed in SAP Section [7.3.1](#), highest dose achieved during the treatment period will be summarized.

[Section 8.6](#) of the SAP describes the summarization and graphical presentation of premature discontinuation due to lack of efficacy or adverse events. This is not included in the protocol but is desired for reporting purposes.

5. Patient Disposition

5.1. Disposition

The number of patients in the safety population will be summarized overall and percentages will be based on the number of enrolled patients.

The number and percentage of patients who consented to participate (i.e. enrolled patients), consented to participate but were not treated, were treated, completed the study, discontinued from the study and the primary reason for premature study and treatment discontinuation will be summarized for all patients who provided consent to participate in the TR03 extension study. Reason for screening failure for patients who discontinued during the Observation Period are not collected on the electronic case report form (eCRF) so will not be summarized. The number and percentage of patients who met failure to improve criterion at any time during the study will also be summarized.

Patient disposition will also be summarized by site.

Patient disposition data will be presented in a data listing.

Reason(s) for exclusion from the safety population will be presented in a data listing.

5.2. Protocol Deviations

Protocol deviations represent departures from protocol-specified procedures and practices. During the course of the study, protocol deviations will be tracked and entered into a single master database that captures the patient number, the type of protocol deviation, and detailed information surrounding the nature and/or circumstance for which the deviation may have occurred.

Protocol deviations will be identified and accounted for prior to database lock. The number and percentage of patients reporting any protocol deviations and the incidence of each deviation type will be summarized by treatment group and overall for the safety population and individual responses will be presented in a data listing for all enrolled patients.

5.3. Eligibility Criteria

For those patients who fail to fulfill any of the inclusion/exclusion criteria or fail to meet the NRS criteria, the criteria not met will be presented in a single data listing for all enrolled patients.

6. Demographics and Baseline Characteristics

6.1. Demographics

Demographics and baseline information will be summarized overall for the safety population.

The demographic characteristics consist of age (years), sex, race, ethnicity, and geographic region (United States (US) or Europe). A patient's age in years is calculated as $\text{FLOOR}[(\text{informed consent date for the TR03 extension study} - \text{date of birth})/365.25]$ expressed as an integer value. The baseline characteristics consist of baseline height (cm) and baseline weight (kg).

Baseline height (cm) and weight (kg) are obtained from the last non-missing evaluation taken prior to the first dose of study medication during the extension study. All other demographic and baseline characteristics (i.e. sex, race, ethnicity and geographic region) were obtained prior to first dose of study medication during the core TR03 study.

Age (years), baseline height (cm) and baseline weight (kg) will be summarized using descriptive statistics. The number and percentage of patients by race (White, Black or African American, Asian, American Indian or Alaska Native, Native Hawaiian or Other Pacific Islander, and Other) and ethnicity (Hispanic or Latino, Not Hispanic or Latino) will also be reported.

Patient demographics and baseline characteristics will be presented in a listing for the safety population.

6.2. Medical History

6.2.1. General Medical History

Past and present medical history data will be coded using the Medical Dictionary for Regulatory Activities (MedDRA, version to be delineated in the clinical study report) and presented in a data listing for the safety population.

For the patients who entered the TR03 Observation Period, medical history with an onset date on or after the TR03 core study randomization date will be presented in a data listing. The listing, thus, will include all TEAEs for the TR03 core study that were converted into medical history in

the TR03 extension study and the non-serious AEs that occurred in the Observation Period of TR03 extension study.

6.2.2. Prurigo Nodularis History

Prurigo nodularis history data for the subset of TR03 core study patients entering the TR03 extension study will be taken from the TR03 core study database as this history was not collected separately for the TR03 extension.

Patients' prurigo nodularis history, collected at the Screening visit during the TR03 core study and consisting of a multitude of categorical responses within various component sub-categories of interest, will be summarized using frequencies and percentages for the safety population.

Responses to all questions will be presented in a data listing for the safety population.

6.2.3. Neurological History

Primary cause of neurological history, collected at Visit 1a/Visit 1b, will be summarized using frequencies and percentages for the safety population. All neurological history information and neurological examination details regarding abnormal findings will be presented in data listings for the safety population.

7. Treatments and Medications

7.1. Concomitant Medications

Patients may receive all clinically indicated medications during the study with the exceptions noted in the study protocol.

A medication's usage will be considered concomitant if it was used by the patient at the time of informed consent or started and/or continued after administration of the study medication.

Concomitant medications, including over-the-counter medications, nutritional supplements, and vitamins will be coded according to the World Health Organization (WHO) Drug Dictionary.

For the purpose of summarizing prior and concomitant medications, incomplete medication start and end dates for medications which are not ongoing will be imputed as follows:

- If the year and month are present and the day is missing, then the day is set to the first day of the month for the start date, and to the last day of the month for the end date.
- If the year and day are present and the month is missing, then the month is set to January for the start date, and to December for the end date.
- If the year is present and the month and day are missing, then the month and day are set to January 1 for the start date, and to December 31 for the end date.
- Data listings will include the recorded and imputed (as described above) start and end dates for each reported medication.

If the medication start date is completely missing and the end date is after the first dose of study drug, then the medication will be classified as concomitant. If the end date is missing, then the medication will be classified as ongoing (concomitant). Medications for which the start and end dates are missing will be classified as concomitant.

The total number of concomitant medications and the number and percentage of patients using at least one concomitant medication will be summarized overall for the safety population.

The number and percentage of all concomitant medications will be summarized by Anatomic and Therapeutic Class (ATC) of WHO drug and preferred term overall for the safety population. Patients will be counted only once within a medication category. If a patient reports taking the same medication more than once, as determined by WHO Drug name, then the medication will be counted only once for that WHO Drug name and patient.

Concomitant medications will be presented in a data listing for the safety population.

Opioid medication usage is summarized and listed with all other concomitant medications. Rescue medications, as described in Section [7.2](#), will be summarized and listed separately from concomitant medications.

